10.2.2. Demographics and Baseline Characteristics

Frequency distributions of gender and race will be tabulated by dose/group. Summary statistics for age, body weight, height, and Body Mass Index (BMI) will be tabulated by dose/group. Comparisons by Chi-Squared or Fisher Exact Test will be conducted, for categorical variables, to assess for baseline differences between groups.

10.2.3. Safety Analyses

All recorded adverse events will be recorded per MDACC guidelines using CTCAE Version 4.0. Frequency of grade ≥ 3 adverse events will be compared via Chi-Squared or Fisher Exact Test.

10.2.4. Efficacy Analyses

Treatment success and clinical benefit will be defined as irCR or irPR or irSD, assessed using irRC (e.g. the best response obtained by a patient). Clinical benefit will be established as having irCR or irPR or irSD > 6 months. Measurements from all imaging, including those obtained during and after re-induction, will be considered in this analysis. Patients will be continuously evaluated for disease response via imaging until they are removed from the study. For secondary objectives a), b), and c), success probabilities will be estimated for each target separately (liver, lung) along with appropriate 95% confidence intervals. Safety comparisons among the groups will be assessed (primary end points) and efficacy comparisons between groups will be assessed with regard to the irRC outcomes while global, in-field irRC will be used for

hypothesis generating using Pearson chi-squared or Fisher exact tests. For secondary objective d) comparisons will be performed between group 2 and 3 as well as per treatment site (liver, or lung).

1. **Global irRC:** irRC that factors all lesions both index and non-index as outlined in 8.3.
2. **In-Field irRC:** irRC in which only SBRT-treated lesions will be considered and non-index lesions arising inside the SBRT PTV
3. **Out-Field irRC:** irRC in which only non SBRT-treated lesions will be considered and non-index lesions arising outside the SBRT PTV

For the secondary objective comparing the response between the arms. With 20 patients per arm, we would have 80% power using a two-sided 10% alpha with a chi-squared test to detect the following differences in response rates between treatment groups 44% vs 10%, 57% vs 20%, 68% vs 30% and 78% vs 40%. To increase statistical power, we may also combine the patients into a single dataset and fit a logistic regression model with response (CR+PR) as the outcome and SBRT dose, target (liver or lung) among other factors (including but not limited to: number of metastatic disease sites, number of prior treatments, primary cancer histology, age, pre-treatment KPS and Royal Marsden Score) as the predictors.

Time-to-event analyses will be conducted via Kaplan-Meier analysis, with comparisons via the log-rank test made with regards to **overall survival**, with analysis beginning at receipt of the first SBRT fraction. At the discretion of the investigators, and if appropriate, a multivariate Cox regression will be done to adjust for (among other factors): number of metastatic disease sites, number of prior treatments, primary cancer histology, age, pre-treatment KPS and Royal Marsden Score.

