2.2. Secondary Objectives

- To determine antitumor activity of ipilimumab therapy with BMS-986156 (30 or 100mg) as well as Nivolumab with BMS-986156 (30 mg) with SBRT treatment for 1-4 lung lesions in both the SBRT treated lesion and non-irradiate tumors.

- b) To determine antitumor activity of ipilimumab therapy with or without BMS-986156 (30 or 100mg) as well as Nivolumab with BMS-986156 (30 mg) with SBRT treatment for 1-4 liver lesions in both the SBRT treated lesion and non-irradiate tumors.
- c) To compare response and progression of the non-irradiated tumors between BMS-986156 with ipilimumab vs BMS-986156 with Nivolumab, using irRC.
- d) To evaluate the predictive potential value of tumor-associated and systemic immune biomarkers for therapy effectiveness and toxicity prediction.
- e) To evaluate whether skeletal mass, neutrophil, neutrophil to lymphocyte ratio, and tumor bulk are correlated with clinical outcomes and adverse events.
- f) To evaluate whether tumor kinetics in combination with clinical correlates can help determine treatment response. The radiological response and clinical data will be analyzed using mathematical and statistical models to identify prognostic groups.
- g) To evaluate whether tumor mutational burden correlates with improved clinical outcomes and response criteria.

3. Background

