8.2.5. Tumor biopsies and serum biomarker evaluation

All patients with accessible tumor will undergo a baseline biopsy of a non-irradiated tumor and a post SBRT biopsy of an irradiated tumor, with low dose radiation, or non-irradiated tumor, as well as a biopsy at the point of progression as determined by the treating physician or PIs of the study. Blood will be drawn with baseline labs, during week 1 of cycle 2 (group 1) or on the last day of radiation treatment (groups 2 and 3), and at progression of disease decided by the discretion of the treating physician and/or study PIs. Blood and tissue biopsies will be mandatory. A tentative calendar is shown in Section 12 in Study Calendar group 1, group 2, group 3.

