8.6 Systemic Biomarkers

The objective of this portion of the study is to correlate systemic serum markers, obtainable by peripheral venous access to patient responses and observed toxicities. Participation in this portion of the protocol is mandatory for all study participants.

Systemic lymphocyte counts obtained from routine CBC with differential will be analyzed and associated with clinical outcomes and toxicities from the lab draws obtained throughout this protocol.

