8.7. Biopsies

The objective of this portion of the study is to correlate histologic/immunohistologic analyses of biopsy samples to patient responses and observed toxicities. Voluntary participation in this portion of the protocol is mandatory for all study participants. All patients will have a tumor assessment on the initial tumor sample via a standard mutation biomarker panel (MD Anderson 46 gene panel, foundation one panel). Assessment can be conducted from any prior biopsy or from the mandatory tumor biopsy sample, if available. When it is feasible (sufficient biopsy material and blood sample), we will examine, tumor mutational burden by whole exome sequencing and TIL profiling by flow cytometry. We will evaluate whether tumor mutational burden and/or TILs correlates with improved clinical outcomes and response criteria. Additionally, we will determine if radiation enhances the tumor DNA availability in blood compared to baseline.

This study will be done in collaboration with Interventional Radiology Investigators. Biopsies can be obtained 1-2 weeks prior to therapy initialization, at week 1 of cycle 2 (\pm 1 week) for groups 1 and 3 or at week 3 of cycle 2 for group 2 OR at any time at the discretion of the treating physician and the PI for research and / or due to medical necessity. See study calendars for tentative schedules (Section 12 Study Calendars).

9. Adverse Event Reporting

An Adverse Event (AE) is the appearance or worsening of any undesirable sign, symptom, or medical condition occurring after starting the study drug even if the event is considered not to be related to the study drug. Medical conditions/diseases present before starting the study drug are only considered adverse events if they worse after starting the study drug. Abnormal laboratory values or test results constitute adverse events only if they include clinical signs or symptoms, are considered clinically significant, or require therapy.

The investigator (or physician designee) is responsible for verifying and providing source documentation for all adverse events and assigning the attribution for all adverse events for subjects enrolled.

The causal relationship to study drug is determined by a physician and should be used to assess all adverse events (AE). The causal relationship can be one of the following:

Related: There is a reasonable causal relationship between study drug administration and the AE.

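### Section 10.2.4 analyses objective d (biomarker prediction) only by comparing groups 2 and 3 and liver with lung, which relates no marker to response or toxicity

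*Combined protocol and SAP*

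**What the plan says.** Section 2.2 states objective d as: "To evaluate the predictive potential value of tumor-associated and systemic immune biomarkers for therapy effectiveness and toxicity prediction". Section 10.2.4 gives its analysis in one sentence: "For secondary objective d) comparisons will be performed between group 2 and 3 as well as per treatment site (liver, or lung".

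Sections 8.6 and 8.7 describe the aim differently. Serum work is meant to "correlate systemic serum markers, obtainable by peripheral venous access to patient responses and observed toxicities", and lymphocyte counts from routine blood counts "will be analyzed and associated with clinical outcomes and toxicities". Tissue work is meant to "correlate histologic/immunohistologic analyses of biopsy samples to patient responses and observed toxicities". Section 8.7 adds: "We will evaluate whether tumor mutational burden and/or TILs correlates with improved clinical outcomes and response criteria". Both sections make participation mandatory for all participants. Neither names a test, a sample time point or an outcome definition.

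Section 8.2.5 places the on-treatment blood draw "during week 1 of cycle 2 (group 1) or on the last day of radiation treatment (groups 2 and 3". Section 8.7 places the on-treatment biopsy at week 1 of cycle 2, give or take a week, "for groups 1 and 3 or at week 3 of cycle 2 for group 2". Section 10.2.1 describes the between-group tests as exploratory.

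**The concern.** A question about prediction needs each patient's marker value set against that patient's outcome. In the stated analysis the marker is compared between treatment groups or between irradiated sites, and response and toxicity do not enter. A marker could differ sharply between groups 2 and 3 and predict nothing. It could also be identical in the two groups and separate responders from non-responders well in each. The trial could therefore carry out its stated analysis of objective d in full and still not answer it.

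The named group contrast also has a problem of its own. On-treatment samples are tied to different events in the two groups, so a difference could reflect when the sample was taken as well as the regimen. Group 1, which gives mandatory blood and tissue too, has no place in that contrast.

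**Working it through.** **1. Is a marker-outcome analysis specified elsewhere in section 10?** Section 10.2.1 plans descriptive statistics that include biomarker response and a global description of outcomes across all three groups. The logistic and Cox models in 10.2.4 name no biomarker among their predictors, although both lists are open-ended. Section 10 therefore gives no method for the correlation stated in 8.6 and 8.7.

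**2. Timing of the samples in groups 2 and 3.** Dosing days come from section 1: 1, 22, 43, 64 in group 2 and 1, 29, 57, 85 in group 3. Blood days come from the section 12 calendar notes. Biopsy weeks come from 8.7 and the calendars. Week 3 of a 21-day cycle 2 is 22 + 14 = day 36 to 22 + 20 = day 42. Week 1 of a 28-day cycle 2 is day 29 to 29 + 6 = day 35.

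| Sample | Group 2 | Group 3 | Difference |
|---|---|---|---|
| Baseline | before first dose | before first dose | none |
| On-treatment blood, 50 Gy in 4 | day 32/33 | day 4/5 | 32 − 4 = 33 − 5 = 28 days |
| On-treatment blood, 60 Gy in 10 | day 40 | day 12 | 40 − 12 = 28 days |
| Doses before that blood | 2 (days 1, 22) | 1 (day 1) | one dose |
| On-treatment biopsy | days 36–42 | days 29–35 | 36 − 29 = 7 days nominally; 36 − 35 = 1 to 42 − 29 = 13 |
| Doses before that biopsy | 2 (days 1, 22) | 2 (days 1, 29) | none |
| Biopsy, days from end of 50 Gy (day 32; day 4) | 4 to 10 | 25 to 31 | about 21 days |
| Biopsy, days from end of 60 Gy (day 40; day 12) | −4 to 2, reading 8.7 alone | 17 to 23 | about 21 days |

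If the 4-fraction course ends on day 33 or day 5, the corresponding interval is one day shorter. If patients with different fractionation are compared, the blood gap runs from 32 − 12 = 20 to 40 − 4 = 36 days. The blood draw is aligned on the end of SBRT in both groups. What differs for blood is time since first dose and number of doses. For tissue, what differs is time since SBRT.

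**3. What a direct analysis could detect.** The plan gives no figure for objective d. Its one power statement, in 10.2.4, concerns response between arms (20 per arm, two-sided 10% alpha, chi-squared, 80% power). With pooled variance under the null,

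power = Φ{ [ |p1 − p2| − 1.645 √(2p̄(1 − p̄)/n) ] / √( [p1(1 − p1) + p2(1 − p2)]/n ) }.

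For 44% v 10% and n = 20, p̄ = 0.27 and power = Φ{(0.340 − 0.231)/0.130} = 80.0%. The other three pairs give 79.4%, 79.4% and 80.7%, so the statement reproduces.

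The same formula can be applied to a marker split at its median, with 10% response in the low half. Both are assumptions. The response rate detectable with 80% power in the high half is:

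- one group (10 v 10): 60.5%
- groups 2 and 3 together (20 v 20): 44.1%
- all three groups (30 v 30): 36.7%

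These are large-sample approximations that ignore stratification. They show what including group 1 gains.

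**4. Number of responders.** Section 3.3 reports 10% out-of-field partial response in the earlier trial of ipilimumab with SBRT. If that held here, an assumption, there would be 0.10 × 20 = 2 responders per group and 0.10 × 60 = 6 overall. Over the lower rates used in the plan's power statement (10% to 40%), the counts run from 2 to 8 per group and from 6 to 24 overall.

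**The case against.** The strongest defence is that 8.6 and 8.7 do commit to correlating markers with response and toxicity, without restriction by group, and that this is an exploratory secondary objective on which no decision depends. That stands as a limit on the consequence. It does not settle the point: the statistical section names a different comparison, and an exploratory analysis should still address its own question.

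The sentence may also be a lettering slip. It sits among the irRC comparisons, and group 2 v group 3 is the ipilimumab v nivolumab contrast of objective c. This cannot be shown from the text. If it is so, the timing issue falls away, but objective d is then left with no analysis of its own in section 10, and the same repair is needed.

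Several stronger readings are tempting, and the documents do not support them:

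- A reader might infer that all samples are 28 days and one dose apart. That holds only for on-treatment blood, and 10.2.4 does not say which time point enters the comparison.
- A reader might infer that lymphocyte counts share this offset. Section 8.6 takes them from routine blood counts throughout the protocol, not from the last-SBRT-day draw.
- A reader might infer that group 2 patients on 10 fractions will be biopsied during SBRT. That follows only from week 3 of cycle 2 in 8.7 read alone. Sections 8.1.3 and 8.2.5 place the biopsy after SBRT, and the group 2 calendar places it at the end of cycle 2. These places need reconciling.
- A reader might infer that group 1's markers go unused. They are outside the objective d contrast, but 8.6, 8.7 and the descriptive statistics in 10.2.1 cover all groups.
- A reader might hope to rescue the group contrast with pre-dose blood counts on matched days. Up to day 85 the scheduled pre-dose days coincide only at days 1 and 85, and by day 85 group 2 has had four combination doses and group 3 three.

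**Conclusion.** The concern holds in this form: the analysis that 10.2.4 assigns to objective d does not answer objective d, and no other part of section 10 supplies a method for the correlation promised in 8.6 and 8.7. The group contrast omits 20 of 60 planned patients. If applied to on-treatment blood, it is confounded by 28 days (same fractionation) and one dose. Applied to tissue, it is confounded mainly by time since SBRT, about three weeks on the nominal schedule. Baseline samples are free of this problem.

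The timing figures assume the nominal schedule. Section 8.7 allows a biopsy at any time at discretion, and its one-week window could put a group 3 biopsy at day 22, before the second dose, whereas the calendar places it after the cycle 2 infusion. The consequence is limited to an exploratory secondary objective: the primary safety objectives and dose decisions are unaffected.

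**What to change.** Replace the objective d sentence in 10.2.4 with the following elements:

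- Compare baseline marker values, and change from baseline to the on-treatment sample, between responders (CR+PR, as in the 10.2.4 logistic model) and non-responders. Make the same comparison between patients with and without a Grade 3 or higher adverse event.
- Do this within each group, then combine groups 1 to 3 with a group-stratified test, for example van Elteren. Stratifying by group keeps the between-group sampling offset out of the comparison.
- Name the response criterion. Global irRC is available in all three groups; in-field irRC is not defined for group 1, which has no SBRT.
- For on-treatment change, count only adverse events that start after the sample.
- Report the results as exploratory, and state that responders per group may be few.
- Label any group 2 v group 3 or liver v lung biomarker contrast descriptive, state the sample time point used, and do not add a matched-day blood count contrast.

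Separately, reconcile the group 2 biopsy timing in 8.1.3, 8.2.5, 8.7 and the group 2 calendar.

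The cost is a change of analysis wording and this reconciliation. No new samples, visits or patients are needed.

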Preliminary safety data on ipilimumab and SBRT: Combining ipilimumab and SBRT was safe with signs of efficacy (1, 25). In this phase I trial, treatments combining liver or lung SBRT at 50 Gy in 4 fractions or 60 Gy in 10 fractions concurrently or sequentially with ipilimumab at 3 mg/kg for 4 doses were considered safe. Two patients (6%) had DLTs, and even though rates of grade 3 treatment-related toxicity were 34% of treated patients, most were self-limiting and managed as an outpatient. Data on efficacy is encouraging, with 10% out-of-field irPR and 23% clinical benefit. Though these data are encouraging, the outcome may be improved by adding another I-O agent to the treatment regimen: we propose to test the safety and efficacy of combining BMS-986156 with ipilimumab + SBRT. However, there are no clinical data available on the safety of BMS-986156 + Ipilimumab. Treatment group 1 will be initiated to determine the safety of combining BMS-986156 (30 or 100 mg) and ipilimumab (3 mg/kg). After BMS-986156 dose determination in group 1, group 2 will be initiated with BMS-986156 (dose as determined in group 1) and ipilimumab plus SBRT. Recently, in our preclinical model of PD-1 resistance we have shown a dramatic improvement in radiation-induced abscopal responses with the addition of anti-GITR antibody. Moreover, an ongoing study (CA009-002) has recently provided human safety data following administration of a flat dose of nivolumab, another checkpoint inhibitor, in combination with BMS-986156, an anti-GITR monoclonal antibody (26). Altogether, these studies suggest that anti-GITR, a T-cell agonist, may potentiate a T cell mediated response and may contribute to abscopal responses observed when SBRT is administered with checkpoint inhibitors such as ipilimumab or nivolumab. These findings likewise prompted us to include additional arms involving concurrent SBRT administration with anti-GITR plus either ipilimumab or nivolumab in this study. Treatment group 3 will be initiated with nivolumab (480mg) plus BMS-986156 (30mg) and SBRT combination therapy.

Our hypotheses are as follows:

1) SBRT targeting a limited number of liver or lung metastasis in conjunction with ipilimumab and BMS-986156 or nivolumab and BMS-986156 combination therapy will result in improved local and systemic disease control.

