10.2.5. Sample Size/Accrual Rate

The maximum planned number of evaluable patients will be 60, with 20 patients being treated in each group (groups: 1, 2 and 3). It is estimated that approximately 3 patients per month will be accrued and an approximate 4 week interval will be allowed between dose levels.

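### The optional pooled logistic model in 10.2.4 names eight predictors for what may be few responders, does not name treatment group, and uses SBRT terms that have no value in group 1

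*Combined protocol and SAP*

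**What the plan says.** Section 10.2.4 first gives the power for comparing response between arms. With 20 patients per arm, "we would have 80% power using a two-sided 10% alpha with a chi-squared test" for four pairs of response rates. It continues that, for more power, "we may also combine the patients into a single dataset and fit a logistic regression model with response (CR+PR) as the outcome". The predictors start with SBRT dose and target (liver or lung). The further factors, in a list stated not to be exhaustive, are "number of metastatic disease sites, number of prior treatments, primary cancer histology, age, pre-treatment KPS and Royal Marsden Score". That makes eight named predictors. Treatment group is not one of them.

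Other sections set the limits:
- Section 10.2.5 caps the trial at 60 evaluable patients, 20 per group.
- Section 10.2.1 confirms that group 1 receives no radiation and describes the between-group tests as exploratory.
- Section 4.1 requires a liver or lung/chest lesion only in groups 2 and 3.
- Section 1 admits metastatic disease from any primary.
- Section 3.3 reports "10% out-of-field irPR and 23% clinical benefit" for the predecessor trial of ipilimumab plus SBRT.

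**The concern.** Three features work against the purpose of the model.

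First, it is offered as a stronger way to compare arms, yet arm is not a listed term. As listed, it does not estimate the contrast whose power it is meant to raise.

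Second, two of its terms have no natural value for a third of the patients, and no coding rule is given.

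Third, the predictor list is long for the number of responders that may occur. When some combination of predictors perfectly sorts responders from non-responders (separation), ordinary maximum likelihood has no finite solution. Software then reports huge odds ratios with uninformative intervals. An open list also leaves the choice of model until after the data are seen.

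What is at stake is an exploratory secondary result. No dose decision, primary endpoint or sample size depends on it.

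**Working it through.** **1. The plan's own figure.** Power = Φ{[|p1 − p2| − 1.645·√(2p̄(1 − p̄)/n)] / √([p1(1 − p1) + p2(1 − p2)]/n)}, with n = 20 per arm and two-sided alpha 10%. For 44% vs 10%, p̄ = 0.27, so (0.34 − 1.645 × 0.1404)/0.1297 = 0.841 and power is 0.800. The pairs 57/20, 68/30 and 78/40 give 0.794, 0.794 and 0.807. The stated 80% is reproduced. No power, event count or response rate is given for the pooled model.

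**2. SBRT terms in group 1.** Suppose dose and target each get a 'none' level. The columns are: intercept, dose none, dose 60 Gy (against 50 Gy), target none, target lung (against liver). The two 'none' columns are identical, so five columns have rank 4 and one coefficient cannot be estimated. The 'none' column that remains is also the indicator of group 1, so adding treatment group creates a further alias. Coding dose as 0 Gy gives dose a value but not target. Treating the terms as missing leaves 60 − 20 = 40 patients.

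**3. Responders per named predictor** (rate × n, then divided by 8). The rates are assumptions. The plan gives none for this model and does not say which irRC version (global, in-field or out-field) defines its outcome.

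| Response rate | Responders, n=60 | Per predictor | Responders, n=40 | Per predictor |
|---|---|---|---|---|
| 10% | 6 | 0.75 | 4 | 0.5 |
| 20% | 12 | 1.5 | 8 | 1.0 |
| 30% | 18 | 2.25 | 12 | 1.5 |
| 40% | 24 | 3.0 | 16 | 2.0 |

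Histology with k levels takes k − 1 coefficients. Four levels therefore give 7 + 3 = 10 coefficients, and 6/10 = 0.6 responders per coefficient at a 10% rate.

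**4. How often there is no finite fit.** Datasets were simulated with no true effects, and complete or quasi-complete separation was detected by linear programming. The covariate distributions are assumed: two binary terms, two counts, age, a performance score, a four-level prognostic score, and histology. Ranges cover several sets of assumptions.

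| Response rate | n=60, 2 histology levels | n=60, 4 levels | n=40, 2 levels | n=40, 4 levels |
|---|---|---|---|---|
| 10% | 19–48% | 65–73% | 48–54% | 88–90% |
| 20% | 2–5% | 19–21% | 4–9% | 47–48% |
| 30% | under 1% | 3–4% | 1–2% | 18–19% |

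Finer histology was run at n=60 with a fixed responder count and one no-SBRT indicator. Five even levels gave 92–96% at a 10% rate, 29–35% at 20% and 10% at 30%. Eight levels gave 100%, 90–92% and 61%. With a random responder count and five uneven levels, the figures at 20% and 30% were 62% and 39%.

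**The case against.** The text is permissive. The model is something that may be fitted, the factors can be read as a pool of candidates, and an open list leaves room to add treatment group. Section 10.2.1 says the comparisons are not formal hypothesis tests, and an analyst would notice separation when it occurred. All of this stands, and it limits the importance of the point. It does not supply a coding rule for group 1 or say how candidates would be chosen.

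A reader might infer that the protocol itself expects 10% response, and so about six responders. It does not. The 10% in section 3.3 is out-of-field response in an earlier trial without BMS-986156. In the power statement, 10% is only the lower rate of the lowest pair. With one arm at the higher rate of a pair and two at the lower, the expected count runs from 20 × 0.44 + 40 × 0.10 = 12.8 to 20 × 0.78 + 40 × 0.40 = 31.6. Section 10.2.4 also counts best response over all imaging, including re-induction, which could raise the count.

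A reader might also infer that 20 patients are bound to be lost. That holds only for a complete-case fit; a 'none' level keeps all 60 at the price of one coefficient.

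Finally, the remedy works with few events too: at 10% response, groups 2 and 3 together have about four responders. That is true. A penalised fit gives finite estimates, not precise ones.

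**Conclusion.** The point holds, as a minor one. The gap in coding group 1 and the absence of treatment group from the named terms do not depend on any response rate. The list is also long at every rate considered: even 40% response gives only 3 responders per named predictor at n=60.

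How often the fit fails does depend on assumptions. Near 10% response it fails in roughly 20–50% of datasets at n=60 with two histology levels and 65–75% with four; at n=40 the figures are about 50% and 90%. At 20% response it is about 2–5% and 20% at n=60, and up to 9% and about 47% at n=40. At 30% it is about 4% or less at n=60 with up to four levels, and about 19% at n=40 with four. It remains high if histology is divided more finely. Covariate distributions and histology grouping are my assumptions, because the plan specifies neither.

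Three stronger conclusions are not supported. The model would not generally fail at higher response rates with coarse histology. It has not been shown that pooling cannot increase power, only that the plan gives no support for saying that it does. Nor has it been shown that every odds ratio would be biased away from 1, since the simulations measured separation and nothing else. The stated 80% power for the chi-squared test is not in question.

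**What to change.** Revise the paragraph in 10.2.4 as follows:
- Include treatment group in the pooled model as the term of interest.
- Estimate SBRT dose and target effects in a separate model restricted to groups 2 and 3.
- Limit each model to one or two further predictors, named in advance, in place of the open list.
- Use Firth penalised logistic regression with profile-likelihood intervals.
- Remove the statement that pooling increases power.

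The cost is SAP wording and standard software. Treatment, data collection and sample size are unchanged. The downside is that fewer factors are examined jointly, and intervals will still be wide if responders are few.
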